## **8 SUBJECT ACCOUNTING AND STUDY DISPOSITION**

A complete accounting of subject participation in the study will be summarized in a table. The purpose of this table is to provide an accounting of subjects from their entrance into the study (after signing informed consent) through their final visit and to account for subject evaluation in major analyses of safety, including reasons for early study termination. The table will display the number of subjects that were enrolled in the study and the number and percentage of subjects who:

- withdrew prior to dosing,

- are included in the safety population
- completed or did not complete the study.
- For those subjects who did not complete the study, the reason for their non-completion, noting the number and percentage of subjects for each reason.

## **9 BASELINE SUBJECT DATA**

### **9.1 Demographic and Other Baseline Characteristics**

Demographic information and other baseline characteristics will be presented using descriptive statistics for the Safety population. Demographic variables will include age, gender, race and ethnicity. Age will be calculated as the age in years from the birth date to the informed consent date and will be rounded down to the nearest integral value. Other baseline characteristics will include height, weight, and body mass index (BMI).

### **9.2 Medical History**

Medical history will be summarized using counts and percentages for the Safety population, and will be mapped to preferred terms and System Organ Class (SOC) using the Medical Dictionary for Regulatory Activities (MedDRA) coding dictionary. The terms will be presented in alphabetical order. Subjects reporting more than one condition in a category will be counted only once for that category.

The subject's ADT history will be summarized.

## **10 PRIOR AND CONCOMITANT MEDICATIONS/NON-DRUG THERAPIES AND PROCEDURES**

Prior medications are medications that are taken and stopped prior to the first application of the study drug. Concomitant medications are those medications that are ongoing at or started after the first application of the study drug. Prior and concomitant medications will be coded using the Anatomical-Therapeutic-Chemical (ATC) classification text from the WHO Drug Dictionary. Medications will be presented by ATC Class and Preferred Term. Prior and concomitant medications will be summarized for the Safety population. Subjects will only be counted one time in each unique ATC Class and Preferred Term category.

If the medication start date is completely missing then the medication will be considered concomitant unless it can be determined that the medication end date occurred prior to the start of the study. If the medication start date is partially missing and the partial date is not sufficient to determine if the medication was taken after the start of the study, then the medication will be considered concomitant for the study unless it can be ruled out by the partial date and/or medication end date.

The non-drug therapies and procedures will be mapped to preferred terms and SOC using the Medical Dictionary for Regulatory Activities (MedDRA) coding dictionary.

## **11 EFFICACY**

Since the study was stopped prematurely, no planned inferential efficacy analyses will be performed for all of the efficacy parameters. However, the all efficacy endpoints including primary, secondary and exploratory parameters (e.g., FSH, LH, SHBG, and PSA) will be summarized by treatment group at each study visit using descriptive statistics. Serum levels of estradiol and estrone will also be summarized by treatment group at each study visit using descriptive statistics. The Expanded Prostate Cancer Index Composite (EPIC)-Hormonal Assessment and the EPIC-Sexual Assessment will be summarized by treatment group at each study visit using descriptive statistics.

## **12 SAFETY**

Safety will be measured by the incidence of AEs, changes in vital signs and clinical safety laboratory results, and electrocardiogram results. All safety analysis will be conducted in the Safety population.

For safety data, the last non-missing pre-administration observation will be used as the baseline value for calculating post-administration changes from baseline. In all summary tables the data will be presented by study dose group.

### **12.1 Exposure to Study Drug**

The number of applications of study drug administered and the total weight of gel applied to each subject will be summarized descriptively by dose group for the Safety population.

### **12.2 Vital Signs**

Vital sign parameters include systolic and diastolic blood pressure, body weight, height, BMI, respiration rate, temperature, and heart rate. Vital sign values and changes from baseline in these parameters will be presented using descriptive summaries by visit.

A shift from baseline analysis of abnormalities (normal, abnormal/clinically significant, and abnormal/ not clinically significant) will also be presented by counts and percentages at each post-administration visit and in an overall view regardless of post-administration assessment time point. In addition, at each time point, the sums of subjects with normal, abnormal CS, and abnormal NCS values at that time point will be summarized. Also, at each time point the sums of subjects with normal, abnormal CS, and abnormal NCS values at baseline and values at that time point will be summarized.

### **12.3 12-Lead Electrocardiogram (ECG)**

A 12-lead ECG was to be performed at Screening and at Week 12, 24, 36, 48, 52, 54/EOS.

ECG parameters include PR interval (msec), QRS interval (msec), RR interval (msec), QT interval (msec), and QTc interval (msec). ECG values and changes from baseline will be presented using descriptive summaries by visit.

A shift from baseline analysis of abnormalities (normal, abnormal/clinically significant, and abnormal/ not clinically significant) will also be presented by counts and percentages at each post-administration visit and in an overall view regardless of post-administration assessment time point. In addition, at each time point, the sums of subjects with normal, abnormal CS, and abnormal NCS values at that time point will be summarized. Also, at each time point the sums of subjects with

normal, abnormal CS, and abnormal NCS values at baseline and values at that time point will be summarized.

## 12.4 Physical Examination

Physical examination results will be summarized at each visit as normal, abnormal/clinically significant or abnormal/not clinically significant, and compared in a shift analysis to the baseline result for each physical examination category and in an overall view regardless of post-administration assessment time point. In addition, at each time point, the sums of subjects with normal, abnormal CS, and abnormal NCS values at that time point will be summarized. Also, at each time point the sums of subjects with normal, abnormal CS, and abnormal NCS values at baseline and values at that time point will be summarized.

## 12.5 Adverse Events

Adverse events (AEs) will be mapped to preferred terms and SOC using the MedDRA coding dictionary.

Summaries of AEs will be also presented based on treatment-emergent AEs (TEAEs), defined as AEs that begin (or if preexisting medical conditions that worsen) after receiving the first application of the study drug. If the adverse event start date is partially or completely missing then the adverse event will be considered treatment-emergent.

The number and percentage of subjects experiencing AEs will be summarized by SOC and preferred term. Subjects will be counted only once at the SOC level and will be counted once for each applicable preferred term; multiple occurrences of the same preferred term for a subject will be counted only once. SOCs, and preferred terms within SOC, will be displayed alphabetically. Similarly, AEs leading to discontinuation from the study will be presented by SOC and preferred term as well. The treatment-related AEs, defined as AEs with relationship of ‘Possibly’ or ‘Probably’ related to the study treatment, will be summarized by SOC and preferred term.

Summaries by SOC and preferred term and maximum intensity or relationship to study treatment will also be provided for AEs. A summary by SOC and preferred term and maximum intensity will be provided for treatment-related AEs as well. Subjects with multiple occurrences of the same SOC or preferred term will be summarized at the maximum intensity or the strongest relationship to study treatment reported for that adverse event. If a subject has an AE with unknown intensity, then the subject will be counted in the intensity category of “Severe”. If a subject has an AE with unknown relationship to study treatment, then the subject will be counted in the relationship category of “Related” even if the subject has another occurrence of the same event with a relationship to study treatment.

Additionally, the number and percentage of subjects experiencing AEs will be summarized by preferred term in an order of decreasing frequency.

The number and percentage of subjects experiencing serious AEs will be summarized by SOC and preferred term.

An overall summary table of the adverse events will be produced. This table displays the number and percentage of subjects who:

- have any treatment emergent adverse events
- have any treatment emergent adverse events at least possibly related to the study drug

- have any treatment emergent adverse events presented by maximum intensity
- have any treatment emergent serious adverse events
- have any treatment emergent serious adverse events at least possibly related to the administration of the study drug
- have any treatment emergent adverse events leading to discontinuation from the study
- have any treatment emergent adverse events leading to death
- have any treatment emergent adverse events leading to death that are at least possibly related to administration of the study drug.

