	
(2) The Kaplan-Meier curve for time to T \geq 50 ng/dL at Week 12 for each treatment group.
 
(3) The Kaplan-Meier curve for time to T \geq 50 ng/dL at Week 24 for each treatment group.
 
All other efficacy parameters (e.g., FSH, LH, SHBG, and PSA) will be summarized by treatment group at each study visit using descriptive statistics. Serum levels of estradiol and estrone will be summarized by treatment group at each study visit using descriptive statistics.
 
Safety variables will be summarized for each dose level and overall. Safety variables include adverse events (AEs), laboratory tests, vital signs, and physical examination findings. Treatment-emergent adverse events are defined as those AEs occurring after the first dose of study drug.

--	---

Table of Contents

Table of Contents	10
List of Figures	11
List of Abbreviations and Terms	12
1.0 Introduction and Rationale	14
2.0 Study Objective	17
3.0 Study Design	18
4.0 Patient Selection and Withdrawal	19
4.1 Inclusion Criteria	19
4.2 Exclusion Criteria	19
4.3 Early Withdrawal of Patients	20
4.4 Patient Replacement	21
5.0 Study Drug	21
5.1 Blinding and Unblinding	21
5.2 Formulation, Packaging, and Labeling	22
5.3 Storage	22
5.4 Dispensing	22
5.5 Dosage and Administration	22
5.6 Study Drug Administration Precautions	23
5.7 Assessment of Compliance	24
5.8 Drug Accountability	24
5.9 Prior and Concomitant Medications	24
5.10 Prohibited Concomitant Medications/Therapies	25
6.0 Study Evaluations	26
6.1 Laboratory Tests	26
6.2 Electrocardiogram	27
6.3 Physical Exam	27
6.4 Vital Signs	27
6.5 Quality of Life Questionnaire	27
7.0 Study Visits	28
8.0 Statistical Plan	37
8.1 Statistical Analysis Plan	37
8.2 Sample Size	37
8.3 Data Management	38
8.4 Study Populations	38
8.5 Handling of Missing and Incomplete Data	38
8.6 Methodology and Conventions	38
8.7 Efficacy Analysis	39
9.0 (Serious) Adverse Event Collection and Reporting	40
9.1 Adverse Event Collection	40
9.2 Reporting of Adverse Events	41
9.3 Assessment of Adverse Event Severity	42
9.4 Serious Adverse Events	43
10.0 Regulatory and Procedural Requirements	44
10.1 Ethical Conduct of the Study	44
10.2 Institutional Review Board	44
10.3 Patient Informed Consent	45

10.4	Advisory Board.....	45
10.5	Investigator Obligations.....	45
10.6	GCP compliance.....	45
10.7	Protocol adherence and investigator agreement.....	46
10.8	Protocol deviations.....	46
10.9	Monitoring of the study.....	46
10.10	Financial disclosure.....	46

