7.2 Study Day 1 (Week 1): Baseline

The evaluations and assessments listed below will be performed within 2 hours prior to dosing with Study Drug on Day 1. An overnight fast is required for the central

laboratory assessments. It is recommended to collect blood samples in the morning (8-10 AM).

- Reaffirmation of participation
- Affirmation of eligibility criteria
- Review of medical history
- Physical exam, including:
 - Height
 - Weight
 - BMI
- Vital Signs: blood pressure, heart rate, respiration rate, and body temperature
- Record AEs
- Record concomitant medications & procedures
- Central laboratory assessments (see [Section 6.1](#) for details)
 - Hematology
 - Blood Chemistry
 - Urinalysis
 - Coagulation Factors
 - Endocrine Assessment
 - Hormone Assessment
 - Biomarkers: Bone & Prostate
 - Efficacy Assessment
 - Pharmacokinetic Assessment
- Administer Quality of Life Questionnaires:
 - EPIC – Hormonal Component
 - EPIC – Sexual Component
- Randomization
- Dispense study drug
- Study drug compliance –weigh canister(s)
- Record study drug administration
- Issue patient’s study drug administration diary
- *Optional* – Low Dose Radiation for the prevention of gynecomastia*

*Timing is at the discretion of the Investigator.

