## 7 DATA AND ANALYSIS CONVENTIONS

Post-text tables and listings will be prepared in accordance with the current ICH Guidelines. The information and explanatory notes to be provided in the “footer” or bottom of each table and listing will include the following information:

1. Date and time of output generation;
2. SAS program name, including the path that generates the output;
3. Any other output-specific details that require further elaboration.

In general, tables will be formatted with a column for each treatment group. The tables for baseline data will be formatted with an additional column displaying the findings for all subjects combined. In general, Row entries in tables are made only if data exists for at least one subject (*i.e.*, a row with all zeros will not appear). The exception to this rule applies to tables that list the termination status of subjects (*e.g.*, reasons for not completing the study). In this case, zeros will appear for study termination reasons that no subject satisfied. The summary tables clearly indicate the number of subjects to which the data apply and unknown or not performed are distinguished from missing data.

Specific algorithms are discussed for imputing missing or partially missing dates, if deemed appropriate, under specific data topics. Imputed or derived data are flagged in the individual subject data listings. Imputed data are not incorporated into any raw or primary datasets. These data are retained in derived (or analysis) datasets.

This section details general conventions to be used for the statistical analyses. The following conventions will be applied to all data presentations and analyses.

- Summary statistics will consist of the number and percentage of responses in each level for categorical variables, and the sample size (n), mean, median, standard deviation (SD) and range (*i.e.* minimum and maximum values) for continuous variables.
- All mean and median values will be formatted to one more decimal place than the measured value. Standard deviation values will be formatted to two more decimal places than the measured value. Minimum and maximum values will be presented with the same number of decimal places as the measured value.
- The number and percentage of responses will be presented in the form XX (XX.X).

- All p-values will be rounded to 4 decimal places. All p-values that round to 0.0000 will be presented as '<0.0001' and p-values that round to 1.0000 will be presented as '>0.9999'.

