### **7.2 Missing Data**

Missing values will not be imputed by estimated values, but treated as missing in the statistical evaluation. All data from all subjects dosed in the study will be included in all listings, plots, summary tables, and statistical analyses when appropriate.

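### SAP 12.5 flags every AE with an incomplete start date as treatment-emergent, even when the known part of the date or the end date places it before the first application; the rule needs one exception clause.

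*SAP*

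**What the plan says.** SAP 12.5 describes TEAEs as "defined as AEs that begin (or if preexisting medical conditions that worsen) after receiving the first application of the study drug". The statistical methods in the Protocol synopsis agree: "Treatment-emergent adverse events are defined as those AEs occurring after the first dose of study drug". The sentence that follows the definition in SAP 12.5 deals with incomplete dates: "If the adverse event start date is partially or completely missing then the adverse event will be considered treatment-emergent". It carries no qualification.

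For medications, SAP 10 also defaults to the on-treatment category when the start date is partial, but with an exception: "unless it can be ruled out by the partial date and/or medication end date".

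Two general SAP conventions bear on dates. SAP 7 leaves date handling to the topic sections: "Specific algorithms are discussed for imputing missing or partially missing dates, if deemed appropriate, under specific data topics". SAP 7.2 rules out imputation: "Missing values will not be imputed by estimated values, but treated as missing in the statistical evaluation". Protocol 8.5 says that missing safety dates will be imputed and leaves the detailed rules to the SAP.

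On collection, Protocol 9.1 and the synopsis start AE reporting at the first dose, and Protocol 9.2.3 excludes pre-existing conditions from the AE form unless they worsen. Protocol 7.2 nevertheless lists AE recording among the Day 1 items under this heading: "The evaluations and assessments listed below will be performed within 2 hours prior to dosing with Study Drug on Day 1". Appendix 1 puts the Day 1 AE mark in the pre-dose column.

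**The concern.** The missing-date sentence does two jobs with one rule. For a date that is truly ambiguous, counting the event as treatment-emergent is a sensible cautious default. For a date that is incomplete but still informative, the same rule discards what is known and can contradict the definition in the sentence before it.

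All eight rows of the overall AE summary in SAP 12.5 are built on the TEAE flag. Safety by dose is part of the primary objective, and the study stopped at 34 men, so the arms are small and a single wrong flag can be visible in a percentage. A wrong flag can only add a TEAE; it cannot remove one.

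**Working it through.** **Which rule governs.** SAP 7 sends date rules to the topic sections, SAP 7.2 imputes nothing, and Protocol 8.5 defers to the SAP. Protocol 8.1 gives the SAP precedence where the two differ. So SAP 12.5 decides the classification of an AE with an incomplete start date. SAP 4.4 and 5.2 appear in the table of contents but were not in the text available to me, and I claim nothing about them.

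**Case check.** Each kind of incomplete date is set against the definition, the rule as written, and a rule with the SAP 10 type of exception.

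| What is known about the AE | Definition in SAP 12.5 | Missing-date rule as written | With the exception |
|---|---|---|---|
| Start month wholly before the month of first application, day missing, no later worsening | Not a TEAE | TEAE | Not a TEAE |
| Start date partial or missing, end date before first application | Not a TEAE | TEAE | Not a TEAE |
| Start month is the month of first application, day missing, end date not earlier than first application | Cannot be decided | TEAE | TEAE |
| Start date wholly missing, no informative end date | Cannot be decided | TEAE | TEAE |
| Began before first application, worsened afterwards | TEAE | TEAE | TEAE |

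The rule as written disagrees with the definition in the first two rows only. The exception removes both disagreements and changes no other row.

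**Can such records reach the database?** Under Protocol 9.1 and 9.2.3 they should not, apart from AEs noted at the Day 1 pre-dose assessment (Protocol 7.2, Appendix 1) or entered contrary to those sections. SAP 12.5 presents TEAE summaries in addition to AE summaries, which suggests that its author allowed for AEs that are not TEAEs.

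**Weight of one wrong flag.** The plan states no figure to reproduce. The inputs are:

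- 34 men randomized (SAP 2).
- Arm sizes are not given. With the equal allocation that the Protocol planned, 34 = 8 + 8 + 9 + 9.

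The overall summary counts men with any TEAE. The shift from one wrongly flagged man is therefore 100/n percentage points if he has no genuine TEAE, and 0 if he has one.

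- n = 9: 100/9 = 11.1 points
- n = 8: 100/8 = 12.5 points
- If the arms hold between 10 and 7 men: 100/10 = 10.0 to 100/7 = 14.3 points
- All arms together: 100/34 = 2.9 points

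The number of AEs with partial dates is not in the documents, so the actual effect cannot be computed.

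**The case against.** The strongest reply is that the Protocol already closes most of the route. AE reporting starts at the first dose, pre-existing conditions stay off the AE form unless they worsen, and Protocol 6.2 to 6.4 send significant pre-dose findings to the ECG, physical examination and vital signs forms. An event properly on the AE form is then already post-dose or worsened, and treating an incomplete date as treatment-emergent fits that. This stands, and it is why the point is minor.

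The Day 1 route is also thin. The list in Protocol 7.2 includes dispensing and recording administration of study drug, so its pre-dose heading cannot apply strictly to every item. Screening is at most 14 days before Day 1, and an event first noted on Day 1 is likely to be recent and easy to date. If only the day were missing, the month would often be that of the first dose, and the event would remain treatment-emergent under either wording. This narrows the route but does not close it, because Appendix 1 marks AEs in the pre-dose column.

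The medication rule is not a perfect parallel. Prior medications are collected on purpose and have to be separated from concomitant ones, whereas pre-dose AEs are not sought. The comparison still shows that the SAP already has suitable wording.

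The rule may be deliberate caution: the same section counts unknown intensity as severe and unknown relationship as related, and it applies to all arms alike. Caution justifies the default for ambiguous dates, which the revised wording keeps. It does not justify flagging an event that the recorded dates show to be pre-treatment.

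A reader might go further and infer that symptoms carried over from earlier androgen deprivation will be counted as effects of the gel, so that tolerability by dose is misstated. The documents do not support that. Such symptoms are pre-existing conditions under Protocol 9.2.3 and are not to be recorded unless they worsen. If they worsen after the first application, they are TEAEs by definition. Nothing in the documents shows that they tend to carry partial dates.

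**Conclusion.** The point holds as a drafting fault with small reach. As written, SAP 12.5 can flag as treatment-emergent an AE that its own definition excludes, and no other visible text in the SAP or Protocol narrows the rule. The number of affected records is unknown, probably small and possibly zero.

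The shift of 11.1 to 12.5 points should not be read as an expected error. It assumes equal allocation of the 34 men, and it applies to one misclassified man who has no genuine TEAE; for a man who has one, the any-TEAE rate does not move. The rows for related events are further protected where the investigator assesses the relationship, because Protocol 9.3 lets incompatible timing support a judgement of unrelated. SAP 7 also has all data listed, so a partial date before the first application would be visible to a reader of the listings. The safety summaries are descriptive, and no test, power or sample size depends on this rule.

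**What to change.** Reword the sentence in SAP 12.5 along these lines: an AE whose start date is partially or completely missing is treated as treatment-emergent unless the available parts of the start date, or the end date, show that it began before the first application of study drug and did not worsen afterwards.

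The cost is one clause in the SAP and one condition in the derivation of the TEAE flag. No data are lost, and ambiguous dates keep their present default. The SAP is already at its final version, so if the tables have been produced, it is enough to check the AEs with partial or missing start dates and state in the clinical study report how many change category, even if the answer is none.
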